Enoxaparin is taken by subcutaneous injection 40 mg once daily for VTE prophylaxis. Apixaban is taken orally as a tablet at a 2.5 mg twice daily for VTE prophylaxis.

Study Duration: 30 months

Participant Duration:

From preoperative clinic visit to 90 days postop, approximately 4 months

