3 STUDY OBJECTIVES AND ENDPOINTS

OBJECTIVES	ENDPOINTS	JUSTIFICATION FOR ENDPOINTS
Primary		
To compare rates of adherence to discharge on enoxaparin vs apixaban	Proportion of days covered (PDC). This will be calculated based on the size of prescription the patient was provided, day of surgery, day of discharge, and how many pills/syringes are remaining at POD30.	This is an objective and quantitative way to measure adherence.
Secondary		
To explore possible reasons for adherence vs non adherence	PROMIS Medication Adherence Scale: a nine-item questionnaire ^{26,27}	This is a validated measure of medication adherence that focuses on the possible reasons for non-adherence
	Participant satisfaction	Participants will answer questions specific to the use of enoxaparin and apixaban at home after RC. These questions were selected based on the clinical experience of the PIs as well as other studies that have examined adherence to enoxaparin and apixaban ^{21,27,28}
	COST-FACIT: a 12-item questionnaire ²	This is a questionnaire that was developed and validated in the cancer population for assessing patient-reported financial distress due to healthcare costs. This questionnaire adds a patient reported component, as simple cost data does not capture how burdensome that cost is to each specific patient
To compare the cost of enoxaparin vs apixaban	Out of pocket cost of prescription for anticoagulant, in dollars	This provides objective measure of the cost comparison between enoxaparin and apixaban. This data combined with adherence data may allow providers to determine the most cost effective option.

OBJECTIVES	ENDPOINTS	JUSTIFICATION FOR ENDPOINTS
Tertiary		
To collect mefficacy and safety data regarding both forms of prophylaxis	Rate of VTE, either PE or DVT Rate of bleeding events, classified as major, clinically relevant nonmajor, or nonmajor.	While data suggest VTE rates are comparable between enoxaparin and apixaban in both non-urologic and urologic studies, the urologic studies are in small populations. We therefore plan to track VTE and bleeding as outcomes to continue contributing to the pool of data. These outcomes would likely have been measured even if they were not outcomes as part of safety monitoring.

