6 STUDY INTERVENTION

Both enoxaparin and apixaban are FDA approved in the setting of VTE prophylaxis and considered standard of care for EP after radical cystectomy. Study personnel will not be directly providing or administering either drug. Rather, the study intervention is the randomization to receive a prescription (with standard clinical counseling) for either of the two forms of prophylaxis. The participant will then be responsible for filling the prescription at their own cost and self-administering the anticoagulant, as would be standard of care after a radical cystectomy. The anticoagulants will be prescribed according to the clinical standard of care: 40 mg injected subcutaneously once daily for enoxaparin and 2.5 mg tablet taken orally twice daily for apixaban. Doses may be reduced in increased based on the patient's medical comorbidity profile (for example weight and CrCl) according to standard prescribing practices. Regardless of the time of day of discharge, participants will be instructed to start self-administering the medication the day after discharge, and continue through post-op day 30.

Participants who fail to receive a prescription for either anticoagulant will be considered not to have received the study intervention. Participants who receive the prescription but report poor compliance with the prescription have still received the study intervention; their poor compliance is tracked as the primary outcome of the study.

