7.1 Adherence & Satisfaction Assessments

The following assessments will be made to assess the adherence and satisfaction with anticoagulants after cystectomy (corresponding to primary and secondary objectives in section 3):

- 1. Medication counting—study personnel will assist with medication counting over the phone. This involves the participant counting the pills/vials of medication they have remaining and then the study personnel will use the date of surgery, date of discharge, and size of prescription found in the medical record to calculate the **proportion of days covered (PDC)**. PDC is the primary endpoint of the study and is the most objective measure of adherence.
- 2. National Institute of Health (NIH) Patient-Reported Outcomes Measurement Information System (PROMIS) Medication Adherence Scale (PMAS)^{29,30} this questionnaire is a validated, nine-item, patient-reported measure of medication adherence that can be either administered by study personnel over the phone or filled out directly in RedCap by study participants who elect to have a secure weblink emailed to them.
- **3.** Patient Satisfaction study personnel will ask a series of independent questions over the phone or participants will answer them directly in RedCap if they elect to have a secure weblink emailed to them. These questions elucidate possible reasons for compliance/noncompliance that are hypothesized specifically to apply to enoxaparin and apixaban.

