9.3 Analysis of the Primary Endpoint

The primary objective of this study is to compare drug adherence between the two study arms, and the corresponding primary endpoint of the study is the proportion of days at home during which the participant took the prescribed anticoagulant. This is defined as the proportion of days covered (PDC).

PDC = number of days of anticoagulant actually taken / number of days of anticoagulant supposed to take

Number of days of anticoagulant actually taken is determined during the POD 30 phone call by asking the participant how many pills/vials they have remaining and then subtracting that from the size of the prescription they were given. Number of days of anticoagulant supposed to take is calculated by subtracting the number of days postop the patient was discharged from 30.

PDC will be compared between the two groups using a **non-inferiority trial design** with difference in proportions test with the following hypothesis:

H₀: Apixaban is inferior to Enoxaparin in terms of the average PDC response.

HA: Apixaban is non-inferior to Enoxaparin in terms of the average PDC response.

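### Section 9.3 counts pills or vials as days without dividing by units per day, so its rule read literally scores full adherence 2.0 on apixaban and 1.0 on enoxaparin; the POD30 count also has no dose cut-off.

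*Combined protocol and SAP*

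**What the plan says.** Section 9.3 describes PDC as "the proportion of days at home during which the participant took the prescribed anticoagulant" and displays it as a ratio of days to days. The numerator is found in the POD30 call by "asking the participant how many pills/vials they have remaining and then subtracting that from the size of the prescription they were given". The denominator is "calculated by subtracting the number of days postop the patient was discharged from 30".

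The regimens in Section 6 are "40 mg injected subcutaneously once daily for enoxaparin and 2.5 mg tablet taken orally twice daily for apixaban", and the synopsis agrees: "Apixaban is taken orally as a tablet at a 2.5 mg twice daily for VTE prophylaxis". Section 6 also allows doses to be adjusted for individual patients. Participants are told to "start self-administering the medication the day after discharge, and continue through post-op day 30".

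Section 7.1 says that "study personnel will use the date of surgery, date of discharge, and size of prescription found in the medical record" to obtain PDC from the count. The Section 3 table lists the same inputs and adds "how many pills/syringes are remaining at POD30". Neither lists dosing frequency. The synopsis gives only a concept: the share of days from discharge to POD30 on which the drug was taken as the prescription directs.

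Section 9.4 adds a binary measure under which a participant is adherent only if every intended dose was taken. Section 9.7 uses that definition for one of the two safety datasets.

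**The concern.** There are two gaps in how the primary endpoint is computed.

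**Units.** The numerator is in tablets or syringes and the denominator is in days. With one unit a day the two coincide. With two units a day the ratio doubles. The written rule therefore gives the wrong value in the apixaban arm, and the error favours non-inferiority and the superiority test that Section 4 places after it.

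**Cut-off.** POD30 is a dosing day, it is inside the denominator, and it is the day of the count. No rule covers doses that are not yet due when the participant counts. A participant who has missed nothing can score below 1. If the binary measure in 9.4 uses the same count, that participant is also classed as non-adherent and drops out of the adherent safety set in 9.7.

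**Working it through.** The plan gives no worked PDC to reproduce. The only figures needed from it are the 85% control value and the 15-point margin in Section 9.3.1, which imply a limit of 0.85 − 0.15 = 0.70.

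**Inputs.** Let d be the postoperative day of discharge and D = 30 − d (Section 9.3). Dosing from the day after discharge through POD30 also covers D days, so the denominator agrees with Section 6. Units per day are 1 for enoxaparin and 2 for apixaban (Section 6). The latest eligible discharge is POD14 (Section 5.2), giving D = 16. The documents give no earliest discharge day; POD4 is assumed, giving D = 26.

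**Units, read literally.** For a share s of prescribed units taken:

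- Enoxaparin: D·s / D = s.
- Apixaban: 2D·s / D = 2s.

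For discharge on POD6 (D = 24), full adherence gives 24/24 = 1.0 and 48/24 = 2.0. The ratio is the same for every discharge day. Other apixaban values are:

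- s = 0.85 gives 1.70.
- s = 0.50 gives 1.0.
- s = 0.425 gives 0.85, equal to the assumed control value.
- s = 0.35 gives 0.70, the non-inferiority limit.

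On the literal reading the true gap at the limit is 0.85 − 0.35 = 0.50, against the intended 0.15. In general the gap is p − (p − 0.15)/2 = (p + 0.15)/2 for control value p. That is 47.5, 52.5 and 55 points for p = 0.80, 0.90 and 0.95.

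**Units, converted.** Dividing the apixaban count by 2 gives (2D/2)/D = 1.0 for full adherence at every discharge day, equal to enoxaparin.

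**Partial days.** Take a participant who takes one of two apixaban tablets every day. The literal rule gives 1.0. Dividing by units per day gives 0.5. The synopsis concept, days on which the prescription was followed, could give 0. Enoxaparin at one injection a day has no such half-day state.

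**Cut-off, after conversion, for a fully adherent participant counted on POD30.** One apixaban tablet pending gives (2D − 1)/(2D). A whole day pending (the injection, or both tablets) gives (D − 1)/D.

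| Discharge | D | One tablet pending | Whole day pending |
|---|---|---|---|
| POD4 (assumed) | 26 | 0.981 | 0.962 |
| POD6 | 24 | 0.979 | 0.958 |
| POD10 | 20 | 0.975 | 0.950 |
| POD14 | 16 | 0.969 | 0.938 |

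The loss is 1/(2D), or 1.9 to 3.1 points, with one tablet pending. It is 1/D, or 3.8 to 6.3 points, with a whole day pending. A call before all of that day's doses costs both arms the same. A midday call costs an apixaban participant 1/(2D) and an enoxaparin participant either nothing or 1/D, depending on when the injection is taken.

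**The case against.** The governing definition in 9.3 is days over days, and the pill-count sentence only says how days are to be found. The regimens are fixed elsewhere in the protocol, trained staff do the calculation, and a proportion near 2.0 would be noticed with the first adherent apixaban patient. Values above 1 do not fit a difference-in-proportions test, and recorded counts can be converted afterwards.

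Most of this stands. A reader might infer that the trial would in fact tolerate a 50-point deficit on apixaban. The documents do not support that: it requires staff and analysts to follow the literal sentence against the stated definition and leave impossible values unchallenged.

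The need for correction remains. No section writes the conversion. Capping values at 1 would hide the fault, since anyone taking at least half the tablets would score 1.0. The repair also involves a choice, because partial days can be scored in more than one way and units per day may differ between patients. In an unblinded trial (Section 4.1) that choice should be written before data are seen.

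On the cut-off, a reader might infer that participants reached after POD30 escape the problem. The documents do not say that the quantity supplied equals the days due. With surplus, doses taken after POD30 would count as taken and could mask missed ones or push PDC above 1. Nor does 9.4 say that its binary measure comes from the count, so the misclassification is conditional.

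**Conclusion.** The calculation rule for the primary endpoint is wrong as written and contradicts its own definition: 1.0 against 2.0 for full adherence. A conversion was probably intended. The 35% figure is a bound on the literal reading at 85% control and a 15-point margin, not a forecast.

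The missing cut-off is a lesser, separate gap. It costs a fully adherent participant 1.9 to 6.3 points, taking POD4 as the earliest discharge (an assumption) and POD14 as the limit. The net effect on the difference between arms is small against the margin. A reader might infer that it favours one drug, but its direction depends on call and dosing times that the documents do not give. The consequence for 9.4 and 9.7 holds only if those sections use the same count.

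**What to change.** 1. In 9.3, divide units taken by each participant's prescribed units per day before dividing by days due, using the regimen as actually prescribed, since Section 6 allows changes.
2. State openly that this measures the proportion of prescribed doses taken, with half credit for a day on which one of two apixaban tablets was taken. A remaining-unit count cannot show which days were complete, so it cannot deliver a strict proportion of days. Align the synopsis, Section 3, 7.1 and 9.3.
3. Set a cut-off so that numerator and denominator cover the same doses. Either use doses due up to the call, recording call time and last dose taken, or use the end of POD30 with a later count that records and excludes any doses taken after POD30.
4. Derive the 9.4 adherent variable and the 9.7 adherent set from the same count.

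The cost is wording in four places plus one or two form fields, and a later call if the second cut-off is chosen. No extra patients or visits are needed. The endpoint is then described as a proportion of doses, which departs from the present wording and should be acknowledged.

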1.1 Synopsis

Title: Comparison of Apixaban versus Enoxaparin for VTE Prevention after

Radical Cystectomy (the CARE trial)

Short Title: Comparison of Apixaban versus Enoxaparin (CARE)

Study Description:

Patients who have undergone radical cystectomy for bladder cancer will be randomized to receive a prescription for either enoxaparin or apixaban to self-administer at home until post operative day 30. Their adherence to the assigned medication will be the primary outcome. Comparisons of patient satisfaction, barriers to adherence, and cost will also be collected. The hypothesis is that adherence, satisfaction, and cost will be greater in the apixaban arm.

Objectives:

1. To compare rates of adherence to discharge on enoxaparin vs apixaban

a. Hypothesis: The apixaban group will exhibit non-inferior adherence, as measured by the proportion of prescribed medication accurately administered.

2. To compare costs of discharge on enoxaparin vs apixaban

a. Hypothesis: The median patient out-of-pocket cost, obtained from the institution's outpatient pharmacy data, is expected to be higher in the apixaban group compared to enoxaparin group.

3. To explore factors contributing to EP adherence

a. Hypothesis: it is anticipated that barriers to adherence to enoxaparin will primarily manifest as operational challenges and patient dissatisfaction, while for apixaban, they will predominantly arise from lack of insurance coverage and cost considerations. To evaluate these barriers, a combination of validated questionnaires and novel measures will be employed.

4. To collect safety and efficacy data on enoxaparin and apixaban

a. Considering that our study size will limit statistical power to detect risk reduction in venous thromboembolism (VTE) and/or bleeding events in either enoxaparin or apixaban, we will instead closely monitor and assess VTE and bleeding events in both treatment arms to contribute to existing studies for possible meta-analysis. This will be achieved

through the implementation of screening questions at each visit.

Primary Endpoint:

To address our primary objective, adherence, the primary endpoint will be measured as the proportion of days covered (PDC), ie the proportion of days between discharge and post operative day 30 during which the participant took their anticoagulant as prescribed.

Secondary Endpoints:

To address our secondary objective of comparing risk factors for adherence/non-adherence, secondary endpoints include:

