8.2 Discontinuation of Study Intervention, Discontinuation from Study

Prophylactic anticoagulation is standard of care after RC and therefore the decision to stop prophylaxis should be situated within a discussion with the treating clinician. The following are anticipated reasons participants may be told to discontinue study intervention (ie stop their anticoagulant) by their treating clinician:

- Development of blood clot. This would require discontinuation of prophylactic dose in favor of therapeutic dose and may involve switching anticoagulant type
- Development of bleeding event
- Development of an adverse event possibly related to the anticoagulant

- Development of a serious adverse event that would make prophylactic anticoagulation contraindicated

If study personnel discover any of these occurrences during study visits and they are not known already to the treating clinician, study personnel will refer the participant to their treating clinician for management, which may include consideration of discontinuation of the anticoagulant.

Study personnel will screen for discontinuation of the study intervention (ie discontinuation of the assigned anticoagulant) that has already occurred at the beginning of the POD30 and POD90 telephone calls. Any instances of study discontinuation will be brought to the attention of the PI and at the discretion of the PI participants who must discontinue the study intervention may remain in the study and complete portions of study visits depending on their reason for anticoagulant discontinuation and length of time they were following study protocol.

Participants may alternatively be discontinued completely from the study for the following reasons:

- Failure to undergo radical cystectomy and pelvic lymph node dissection
- Failure to be discharged on prophylactic anticoagulant
- Failure to be discharged by POD14
- Lost to Follow Up, defined as failing to complete the study visit despite three attempts to contact the participant via phone and/or email
- Participant request; participants are free to withdraw at any time

Any study discontinuation or discontinuation of the study intervention will be documented, including the date and reason for discontinuation. All instances will be reviewed by PI.. Participants who are discontinued will not be replaced.

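### PDC scores any drug no longer in the participant's hands as taken, and the protocol text neither asks for unused units to be kept nor feeds a stop date into the formula

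*Combined protocol and SAP*

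**What the plan says.** The Synopsis (1.1) defines the primary endpoint as "the proportion of days between discharge and post operative day 30 during which the participant took their anticoagulant as prescribed". Section 9.3 turns this into a ratio. The numerator comes from the POD30 call, by "asking the participant how many pills/vials they have remaining and then subtracting that from the size of the prescription they were given". For the denominator, "Number of days of anticoagulant supposed to take is calculated by subtracting the number of days postop the patient was discharged from 30".

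Section 7.1 describes the same procedure: "This involves the participant counting the pills/vials of medication they have remaining", after which staff apply the "date of surgery, date of discharge, and size of prescription found in the medical record". Staff help with the count by phone.

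The dosing instruction in section 6 is that "participants will be instructed to start self-administering the medication the day after discharge, and continue through post-op day 30". It does not mention keeping what is left over.

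Two other items bear on adherence:
- Section 8.2: "Study personnel will screen for discontinuation of the study intervention" at the start of the POD30 and POD90 calls, and the date and reason are documented.
- Section 7.1: PMAS, a nine-item self-report scale, is collected as a secondary endpoint.

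Neither 7.1, 8.2 nor 9.3 links either item to the calculation of PDC.

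**The concern.** The endpoint is meant to capture days on which the drug was taken. The formula captures units that have left the participant's possession. The two agree only if every missing unit was swallowed or injected. Where unused drug has been disposed of, the error always runs towards higher adherence, and it is largest for those who took least.

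This matters because 3 and 7.1 rest the primary comparison on the count being objective, and 4.1 cites the counts as part of the reason that blinding of investigators is unnecessary. Abandonment of the regimen is also what the trial is about: 2.1 reports that about 20% of surveyed prescribers see problems with adherence and refusal of injections.

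If the binary endpoint in 9.4 is taken from the same count, the error carries into it and into the safety analysis of adherent participants in 9.7. Discarded units cannot be recounted later, so the gap cannot be repaired at analysis.

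**Working it through.** **Inputs from the documents.** The control PDC is 85%, the margin 15 points, one-sided alpha 0.05, power 80% and 45 per arm (9.3.1). The formula is from 9.3.

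**Assumptions.** Discharge is on POD7 with supply equal to days due. The stopping day, the disposal rates and the SD of PDC are also assumed, because the documents give none of them.

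**The plan's own figure and the SD.** No SD for PDC is stated.
- Treated as a mean, 45 per arm corresponds to SD = 0.15 / [(1.645 + 0.842) × √(2/45)] = 0.286.
- Treated as a simple proportion with equal arms, SD = √(0.85 × 0.15) = 0.357. Then n = 2 × 0.85 × 0.15 × (1.645 + 0.842)² / 0.15² ≈ 70.1, or 71 per arm. The stated 45 is not reproduced on that reading.

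The present point does not depend on which is right, so both SDs are carried below.

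**One participant.**
- Days due = 30 − 7 = 23.
- Takes 11 days, has none left: true PDC = 11/23 = 0.48; scored (23 − 0)/23 = 1.00.
- Overstatement = 12/23 = 0.522.
- If supply exceeds days due and nothing is left, the score exceeds 1 and the anomaly is visible.

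**One arm's mean.** If 5% of an arm does this, the mean rises by 0.05 × 0.522 = 2.6 points; if 10%, by 5.2 points.

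**The difference between arms.** The answer depends on the pattern of disposal.

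1. *Same share of discarders, same shortfall, in both arms.* Both means rise equally, so the difference changes by 0.

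2. *A fraction q of untaken drug is discarded in both arms.* Observed PDC = 1 − (1 − q)(1 − true PDC), so the observed difference is (1 − q) × the true difference. With true values of 85% and 70%, exactly at the margin, the chance of declaring non-inferiority is Φ[(0.15 − observed deficit)/SE − 1.645]. Here SE = SD × √(2/45), which is 0.0603 for SD 0.286 and 0.0753 for SD 0.357.

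| q | Observed deficit (points) | SD 0.286 | SD 0.357 |
|---|---|---|---|
| 0 | 15.0 | 5% | 5% |
| 10% | 13.5 | 8% | 7% |
| 20% | 12.0 | 13% | 11% |
| 30% | 10.5 | 18% | 15% |

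3. *Disposal in one arm only, by 10% of that arm (5.2 points), SD 0.286.*
   - Apixaban inflated, true deficit at the margin: Φ(0.0522/0.0603 − 1.645) ≈ 22% instead of 5%.
   - Enoxaparin inflated, arms truly equal: Φ[(0.15 − 0.0522)/0.0603 − 1.645] ≈ 49% instead of 80%.

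   The bias can therefore run in either direction.

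**The case against.** The strongest reply is that the protocol already looks for early stoppers. The discontinuation screen in 8.2 takes place at the same call as the count and records a date, and PMAS gives a second view of adherence. A reader might infer that the count is the only adherence information collected; the documents do not support that. The narrower point stands: neither source alters PDC. Section 8.2 also frames stopping mainly as a treating clinician's decision, and section 6 treats poor compliance as the outcome itself, so a participant who simply stops may not be logged as a discontinuation.

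Four other inferences go too far.
- *Participants are never told to keep leftovers or asked about disposal.* The call script, the content of the counselling and the consent pages are not shown. Only the visible protocol can be said not to specify it. The formula has no term for disposed units in any case.
- *Early stoppers discard most.* This is plausible, but no passage documents it. The count is scheduled for POD30, the last treatment day, which limits the time for disposal. Repeated contact attempts can lengthen it: 8.2 defines loss to follow-up as "failing to complete the study visit despite three attempts to contact the participant via phone and/or email".
- *The 2.6-5.2 points are bias in the comparison.* They are a shift in one arm's mean and cancel if both arms behave alike.
- *The flaw always favours non-inferiority.* Shrinkage does so only when apixaban is truly worse. If apixaban is truly better, shrinkage hides part of its advantage, which matters for the superiority step in section 4.

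It is also fair to say that undetected disposal is a general limit of unit counts, and that recalled disposal is softer than a count. That argues for a modest remedy, not for leaving the formula as it is.

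**Conclusion.** The point holds as a gap between the endpoint and its formula. As written, 9.3 can score an early stopper as fully adherent, and the stop date that 8.2 already collects is not used to prevent it. For one participant the overstatement can be about half of the scale (0.48 scored as 1.00, if supply equals days due).

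The effect on the comparison cannot be fixed from the documents, because no disposal rate is given. It ranges from nil (equal shares and shortfalls) to a rise in false non-inferiority from 5% to about 8-18% (10-30% of untaken units discarded, SD 0.286, true deficit at the margin; about 7-15% with SD 0.357). If disposal differs by arm, it can go either way.

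A reader might also infer that every such person is misclassified as adherent in 9.4. That does not follow, because 9.4 names no data source. It would be so only if the binary measure is derived from the same count. The change is worth making because it is cheap and cannot be made retrospectively; the documents do not show that the primary result would be overturned.

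**What to change.** - **Section 6:** instruct participants, identically in both arms and at both sites, to keep all unused tablets or syringes until the POD30 call.
- **Section 7.1:** at that call, ask how many units were discarded, lost, returned or given away. Extend the discontinuation question in 8.2 to record a last-dose date for any stop, including one the participant made alone.
- **Section 9.3:** set units taken = units obtained − units remaining − units otherwise disposed of, then convert to days. Where the disposed number is unknown, or the count conflicts with the last-dose date, cap days taken at that date.
- **Section 9.4:** derive the binary endpoint from the same corrected count.

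The cost is one sentence of instruction, one new question and one extended question in an existing call, and a revised formula. There are two small downsides. The number of disposed units relies on recall. The retention instruction may slightly prompt adherence, though by design equally in both arms.

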9.4 Analysis of Secondary Endpoints

The following secondary endpoints will be assessed to further characterize adherence and also related elements of satisfaction and cost, though analyses of these related elements are not dependent on findings of the primary endpoint.

- 1. A binary measure of adherence: adherent vs non-adherent. Adherent is defined as taking *all* intended anticoagulant. Adherence in this definition will be compared using a test of proportions (proportion of patients in one study arm that were "adherent" vs proportion of patients in the other arm that were "adherent") within the ITT and population.
- 2. Cost of the medication. There are several measures of cost that will be studied as endpoints, including overall medication cost, cost paid by insurance, and most importantly participant out of pocket cost. Cost will be measured in dollars and reported as median and as mean depending on the presence of outliers. This will be collected from pharmacy review of prescriptions. Cost will be compared using a rank sum test.
- 3. Scores on the two validated questionnaires given: PROMIS and COST. These validated questionnaires both have scoring systems and a t test of the average score of participants in each arm will be compared (ie average score on COST for participants in apixaban arm vs average score on COST for participants in enoxaparin arm). A rank sum test will be used if distributions have outliers.

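### The PDC denominator in 9.3 runs to POD30 for everyone, with no rule for clinician-ordered stops, so a safety difference between arms can appear as an adherence difference

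*Combined protocol and SAP*

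**What the plan says.** Section 9.3 defines the endpoint as a ratio: "PDC = number of days of anticoagulant actually taken / number of days of anticoagulant supposed to take". The denominator has one formula and no exception: "Number of days of anticoagulant supposed to take is calculated by subtracting the number of days postop the patient was discharged from 30". The numerator comes from a single count at the POD30 call, made by "asking the participant how many pills/vials they have remaining and then subtracting that from the size of the prescription they were given". Section 6 gives the matching instruction: "participants will be instructed to start self-administering the medication the day after discharge, and continue through post-op day 30". It also says that poor compliance with the prescription is what the primary outcome tracks.

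The synopsis describes the endpoint as "the proportion of days between discharge and post operative day 30 during which the participant took their anticoagulant as prescribed".

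Section 8.2 introduces its list of stops with: "The following are anticipated reasons participants may be told to discontinue study intervention (ie stop their anticoagulant) by their treating clinician". The list covers a clot, a bleed, a possibly related adverse event, and a serious adverse event that makes prophylaxis contraindicated. The date and reason of each stop are recorded. The PI decides whether these participants stay in the study and which parts of the visits they complete. Section 7.4.1 says that a VTE may end the study intervention but does not end study participation.

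Section 9.7 analyses PDC in all randomized participants, treats missing data as random, and leaves it out. The binary measure in 9.4 begins "Adherent is defined as taking" and goes on to require all of the intended drug. It does not say whether intended days end at a stop order.

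**The concern.** Once the treating clinician has stopped the prophylactic drug, the participant is no longer supposed to take it. The 9.3 formula still counts those days as days it should have been taken. Following the order therefore lowers PDC exactly as forgetting or refusing doses would, although sections 6 and 9.3 present the endpoint as a measure of compliance.

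The comparison between arms is what is at stake. If one drug led to more bleeds, clots or other events that prompt a stop, its mean PDC would fall even if every participant did as told. The non-inferiority test, and the superiority test that section 4 plans if non-inferiority is met, would report that fall as a difference in adherence.

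There is also a second route. If the POD30 count is not done, the participant drops out of the analysis as missing at random, although the reason is an event possibly related to treatment. The same clinical course could thus be scored low or vanish, case by case, in an open-label trial.

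**Working it through.** **1. Is the formula right when nobody orders a stop?** Section 6 has dosing run from the day after discharge through POD30. For discharge on POD6 that is POD7 to POD30, or 24 days, and 30 − 6 = 24. The formula is correct for anyone never told to stop.

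**2. One participant, stop ordered.** The discharge and stop days are assumed, and every dose is taken until the stop.

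| Discharge | Days taken before stop | PDC under 9.3 | PDC with denominator ended at stop |
|---|---|---|---|
| POD6 | 9 (POD7 to POD15) | 9/24 = 37.5% | 9/9 = 100% |
| POD7 | 7 | 7/23 = 30% | 7/7 = 100% |
| POD5 | 10 | 10/25 = 40% | 10/10 = 100% |
| POD14 (latest allowed) | 3 | 3/16 = 19% | 3/3 = 100% |

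In an arm of 45 (section 9.3.1; used here only as the planned arm size), one participant like the first row lowers the arm mean by (1 − 0.375)/45 = 0.0139, or 1.4 points.

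**3. Arm level.** Inputs: adherence of 85% (9.3.1), and stops at mid-course (assumed). A stopped participant scores 0.85 × 0.5 = 0.425 under 9.3 and 0.85 with the denominator ended at the stop, a loss of 0.425. The shift in the difference between arms is the excess stop rate × 0.425.

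| Excess of stops in one arm (assumed) | Shift in PDC difference | Share of 15-point margin |
|---|---|---|
| 2 points | 0.9 points | 6% |
| 5 points | 2.1 points | 14% |
| 10 points | 4.3 points | 28% |
| 20 points | 8.5 points | 57% |

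An excess in the apixaban arm makes non-inferiority harder to show; an excess in the enoxaparin arm makes it easier. Equal rates lower both arms and give no fixed direction.

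**4. A rough gauge from the documents.** The retrospective urologic comparisons in section 2.2 give VTE or DVT rates of 0% v 3.6%, 0% v 3.1%, and 1/29 (3.4%) v 3/37 (8.1%) for DOAC or apixaban v enoxaparin. The differences are 3.6, 3.1 and 4.7 points. If every such event caused a mid-course stop, the shifts would be 3.6 × 0.425 = 1.5, 3.1 × 0.425 = 1.3 and 4.7 × 0.425 = 2.0 points. This covers clots only, not bleeds or other adverse events, and the studies were not randomized.

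**The case against.** The strongest reply is that a fixed window is a legitimate choice. Counting coverage to POD30 whatever the reason for stopping is a treatment-policy approach, and it suits a pragmatic trial with an intention-to-treat primary analysis. Ending the denominator at a stop conditions on an event after randomization. It requires someone to label each stop in an unblinded trial, and it gives full weight to very short courses: three doses before an early stop would score 100%. These costs are real and should shape the fix. They do not settle the matter, because the plan nowhere says that it adopts treatment policy, and its own terms concern compliance.

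The size may also be small. Section 2.1 cites a 400-patient randomized trial with no difference between these drugs in major bleeding or VTE, and section 4.2 calls bleeding a low risk at this dose. That stands: the effect is probably a few points against a 15-point margin.

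Four stronger readings are tempting, and the documents do not support them:

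- A reader might infer that the synopsis flatly contradicts 9.3. It does not: its sentence sets the same discharge-to-POD30 window. The tension is with the words about taking the drug as prescribed, with the label of the 9.3 denominator, and with the reference to poor compliance in section 6.
- A reader might infer that these participants are labelled non-adherent. PDC is a proportion, so their score is reduced. The binary measure is affected only if intended days in 9.4 run to POD30.
- A reader might infer that all of them remain and are scored low. PI discretion means that some may have no count.
- A reader might infer that home supply used under a therapeutic order inflates PDC. No section describes this, and 8.2 notes that the drug may be switched.

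**Conclusion.** The concern holds as a missing rule in the primary endpoint. Section 9.3 gives a denominator that does not fit participants whose clinician stops the drug, although 8.2 anticipates them. Depending on whether the count is done, they lose every later day or leave the analysis.

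The individual effect is large (37.5% instead of 100% in the example). The effect on the comparison is unknown, because the documents give no stop rates by arm. Assuming mid-course stops and 85% adherence, it is about 2.1 points per 5-point excess of stops in one arm. That is modest against the 15-point margin, but it matters more for the planned superiority test. Nothing in the documents establishes a direction of bias or shows that the non-inferiority conclusion would be overturned.

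One further consequence is conditional. Section 9.7 repeats the safety analyses in participants who meet the 9.4 definition of adherent. If intended days run to POD30, people stopped for a bleed or clot leave that set because of the event it is meant to count.

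The sponsor should correct this before analysis.

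**What to change.** - **Section 9.3:** end the days supposed to take at the earlier of POD30 and the documented date of a clinician-ordered stop or replacement of the prophylactic order. Keep participant-initiated stops as missed days.
- **Synopsis and 9.4:** align the endpoint window and the meaning of intended days with this end date.
- **Section 8.2:** obtain the POD30 count for all such participants, so that none is lost through case-by-case discretion.
- **Sensitivity analysis:** prespecify PDC with the fixed POD30 denominator. If the sponsor does want treatment policy as the primary approach, it should say so and swap the two.

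The cost is a few sentences. Section 8.2 already records the date and reason of every stop. For a plain stop the POD30 count still works, because the remaining supply no longer changes. If supply was used under a new therapeutic order, the date of the change can come from the chart or from one question at the POD30 call.

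The main downside is that each stop must be classified as clinician-ordered or participant-initiated in an open-label trial. Take this from the medical record, ideally without reference to the PDC result. Early stops will also give short denominators, which the sensitivity analysis helps to put in context. The change affects scoring only and alters no clinical rule.
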